The current study proposes to interrogate these mechanisms and how they differ as a function of sex and age. We will first leverage our ongoing experimental study examining endotoxin-induced depression in older adults (R01AG051944, PI [name]) to test for sex differences in endotoxin-induced alterations in negative and positive affective processes among older adults. This study is expected to recruit 160 subjects aged 60-80 years (80 females vs. 80 males). We next propose to recruit an additional 40 healthy premenopausal women (age 30-40) to participate in this supplemental study, which will allow us a complementary test of age as a vulnerability factor for endotoxin-induced depression and associated affective responding mechanisms in females. Specifically, in this randomized placebo-controlled experimental study, we aim to:

1. Examine the effect of female sex on affective responses to endotoxin in older adults. We hypothesize that, compared to males, females will present with higher negative affective responses and lower positive affective responses to endotoxin.

2. Examine the effect of age on affective responses to endotoxin in females. We hypothesize that, compared to older females, younger females will present with higher negative affective responses and lower positive affective responses to endotoxin.

3. Examine the correlation between inflammatory response and affective response to endotoxin according to sex and age. We hypothesize that the correlations between circulating proinflammatory cytokines and affective responses following endotoxin administration will be stronger in older females than in older males and in younger females than in older females.

Exploratory Aim: Examine the prospective associations between acute affective responses to endotoxin and long-term development of depressive disorders over 2 years, extending our preliminary findings.

RESEARCH STRATEGY

A. SIGNIFICANCE

A.1. Female Sex: A Vulnerability Factor for Inflammation-Induced Depression?

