
C.2.2. Overview of study design

To address Aim 1, examining sex differences in affective sensitivity to inflammation among older adults, we will select a total of 80 healthy older adults aged 60-80 years (40 males and 40 females), who are absent of current psychiatric illnesses, insomnia, and medical conditions (e.g., inflammatory disorders), into a placebo-controlled, randomized, double-blind, experimental inflammatory challenge protocol. Participants will be randomly assigned to receive either endotoxin (n=40) or placebo (n=40) in a between-subjects manner, stratified by sex. To address Aim 2, examining age differences in affective sensitivity to inflammation among females, we will recruit an additional 40 healthy premenopausal adult women (age 30-40) to be randomly assigned to receive endotoxin (n=20) or placebo (n=20).

For all participants, administration of endotoxin (0.8 ng/kg body weight vs. placebo), will be followed by self-report measures of depressed mood, negative and positive affect, and sickness symptoms (e.g., fatigue) assessed hourly over a 12-hour period; objective ratings of depressive symptoms by an observer blind to condition will be made every 2 hours. Behavioral tasks will be administered to coincide with peak onset of depressed mood, which we have previously shown to occur at 2 hours in both older and younger adults. Our prior protocol duration was 6 hours, but the current proposal will test for the presence of delayed termination of response^{57,58} and extend protocol duration to 12 hours. At baseline and starting two hours post-injection, at peak cytokine- and depressed mood responses, participants will complete the Probabilistic Reward Learning task⁵⁰⁻⁵², the Effort Expenditure for Reward Task,⁵⁹ the Social Choice task (i.e., intersection of reward

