Baseline assessment procedures (prior to experimental protocol): In a face-to-face interview, the following domains will be assessed: psychiatric history, insomnia, negative and positive valence, biobehavioral and medical factors (i.e., demographic; medical/medication histories; health status) and psychosocial stress and social support. The SCID-5 interview will determine the presence of past history of depression, and the absence of current depressive disorder and other psychiatric diagnoses. We have over two decades of experience in the administration of the SCID, train to criterion validity, obtain diagnoses in a weekly consensus meeting to maintain reliability and criterion validity, and use videotaped interviews for quarterly monitoring of validity/reliability of interviewers. Depressive/anxiety symptoms will be assessed using Beck Depression Inventory (BDI-II), Beck Anxiety Inventory (BAI),^{69,70} and Inventory of Depressive Symptomatology.⁷¹

Negative and positive affect valence: Affect valence characteristics might be related to variable affect response following inflammatory challenge, and will be assessed by self-report questionnaires including the *Behavioral Inhibition and Activation Systems (BIS/BAS) Scale*⁷² (i.e., punishment sensitivity; drive, fun seeking, reward responsiveness); *Temporal Experience of Pleasure Scale*⁷³ (i.e., anticipatory, consummatory pleasure); and *Response Style Questionnaire Ruminative Responses Scale*⁷⁴ (i.e., tendency to ruminate in response to symptoms of negative emotion).

Biobehavioral and medical factors will be assessed that might be associated with inflammation, depression risk, or both, including *demographic information*; *biobehavioral confounds of inflammation*⁷⁵ such as alcohol use, smoking, BMI, and physical activity (i.e., *Godin Leisure-Time Exercise Questionnaire*⁷⁶); and *medical factors* (i.e., *Charlson Co-Morbidity Index*, *Chronic Disease Score*⁷⁷) and health functioning (i.e., *Medical Outcomes Study Short-form [SF-36]*⁷⁸⁻⁸⁰). We also assess menstrual history and status.

Psychosocial factors will be assessed including number and perceived threat of recent life stresses (i.e., *Perceived Stress Scale*⁸¹) and subjective social isolation that is associated with depression, sleep

disturbance and inflammation (i.e., 10-item Revised UCLA Loneliness Scale,⁸² Interpersonal Support Evaluation List,⁸³ short form Social Support Questionnaire [SSQ]⁸⁴).

C.2.6. Experimental Measures

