Participants who complete the experimental session will be followed up by telephone over 2 years for the assessment of depressive symptoms and disorders. A research assistant will call participants every 3 months for administration of the PHQ-9. If their responses suggest depression (i.e., PHQ-9 ≥ 5), the project coordinator will conduct the SCID-5-RV over telephone. We have successfully conducted such a telephone follow-up in an ongoing depression prevention Study (R01AG026364, PI [name]). Telephone administration of the SCID has been found acceptable and comparable to in-person administration.^{101,102}

C.2.8. Statistical Analyses

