All measured variables will be assessed for distributional qualities and transformed if necessary for use in the selected statistical models. Adequacy of random assignment and matching will be tested using t-tests and chi-square tests as appropriate. All pre-classification variables (age, BMI, insomnia, medical comorbidity, prior depression history) and baseline values of outcomes will be compared; those that are significantly different between females and males (at $P < 0.15$) will be considered for inclusion as covariates in the main analyses. Missing data patterns will be analyzed to assess the potential for biased parameter estimates; missing data will not be imputed as the methods selected allow for missing data under common missingness assumptions. The basic design for Aim 1 is a 2 group (females vs. males) by 2 condition (endotoxin vs. placebo) independent balanced analysis of variance (ANOVA) with one or repeated outcome measures (times: T_{hr} where $hr = 0$ for baseline, 0.5 to 12 post-infusion; peak cytokine concentration at T_2)¹², conducted with linear mixed models (LMM). The number of repeated measures varies by assessment. The key results are the main effects of sex, condition, and their interaction; for those analyses with repeated measures, the two main effects and interaction will further interact with the time variable. Other planned analyses include lagged (time series) relationships between cytokine outcomes and affect measures via general linear modeling (GLM). Standard pharmacokinetic parameters (e.g., AUC, C_{MAX} , T_{MAX}) may also be used to create summary cytokine and affect profile outcomes. Finally, covariates (i.e., pre-classification variables such as prior depression history, insomnia, or baseline CRP) will be tested if appropriate (i.e., $p < 0.15$) to assess the robustness of the results and further explicate the findings. **Aim 1** is tested with LMM for the following outcomes (timepoints): POMS Depression, DACL, Social Disconnection (T_0 , $T_1 - T_{12}$), Observer rated depression (T_0 , $T_{2,4,6,8,12}$), Cyberball Social Exclusion Task (T_2), Emotion Tasks (T_0 , T_2), Social Support Questionnaire (T_0 , T_2), Social Choice Task (T_0 , T_2), Reward Response (T_0 , T_2), Reward Learning (T_0 , T_2), and Reward Motivation (T_0 , T_2). The basic design for **Aim 2** is identical to Aim 1 but using age as the group variable (young females vs. older females) instead of sex. **Aim 3** is restricted to the endotoxin condition to examine the correlations between inflammatory responses and affective responses to endotoxin according to sex and age. These correlations will be examined using mixed-effects model linear regression, and cytokines and depressed mood, including excess negative affect and deficits in positive affect, will be entered in the regression models in their longitudinal format, thus reflecting all the measurements performed during the study (T_0 , $T_1 - T_{12}$). **Exploratory Aim** is tested using mixed-effects logistic regression, separately in the endotoxin and placebo groups, because the outcome (depressive episodes) is a binary variable repeatedly measured over 2 years. The predictor variables include the sum of POMS depression during 12 hours of experimental session, Cyberball Social Exclusion Task (T_2), Emotion Tasks (T_2), Social Choice Task (T_2), and Reward Tasks (Response, Learning, Motivation, Sensitivity) (T_2).

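### Exploratory Aim: the scoring of an ongoing or recurrent depressive episode across the 3-monthly calls is undefined, and scored as status at each call the planned model mixes onset with duration

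*Combined protocol and SAP*

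**What the plan says.** - **Question.** Specific Aims, Exploratory Aim: "Examine the prospective associations between acute affective responses to endotoxin and long-term development of depressive disorders over 2 years".
- **Entry status.** C.2.5 uses the SCID-5 to establish "the absence of current depressive disorder and other psychiatric diagnoses". Past depression is allowed.
- **Follow-up.** C.2.7: "A research assistant will call participants every 3 months for administration of the PHQ-9". If the PHQ-9 is 5 or more, "the project coordinator will conduct the SCID-5-RV over telephone". The period that this interview covers is not given.
- **Analysis.** C.2.8: the aim "is tested using mixed-effects logistic regression, separately in the endotoxin and placebo groups", and the reason offered is "because the outcome (depressive episodes) is a binary variable repeatedly measured over 2 years".

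The documents do not define a first onset or a risk set. They have no rule for an episode still present at the next call and none for when a later positive call is a new episode. They give no event count, episode rate or power for this aim.

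**The concern.** The aim speaks of development. Since nobody has a current depressive disorder at entry, a participant's first positive call marks a new episode. Later positive calls may be the same episode continuing. The stated reason for the mixed model is that each participant carries a repeated yes/no measurement, and nothing in C.2.7 or C.2.8 takes a participant out of the records after a positive call. The natural reading is therefore status at each call.

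On that reading the model estimates the odds of being in an episode at a call, which depend on how often episodes start and on how long they last. The subject-level random effect allows for correlation within a person but does not change that target. An acute response related only to slower recovery could then be reported as predicting who develops depression. Section A.4 intends the result to support prevention trials, where that distinction matters. Two analysts could also build different datasets from the same calls.

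**Working it through.** There is no stated figure to reproduce, so the check has three parts. Incidence, duration and effect sizes below are assumptions; the documents give none.

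**1. Inputs from the documents.** Calls: 24 / 3 = 8. Older adults: "Participants will be randomly assigned to receive either endotoxin (n=40) or placebo (n=40) in a between-subjects manner, stratified by sex" (C.2.2). Younger women: 20 per condition (C.2.2). Per condition: 40 + 20 = 60, taking the 80 older adults without insomnia plus the 40 younger women.

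**2. Records per episode if status is scored at each call.** An episode of fixed length D months spans D/3 calls on average, ignoring the end of follow-up: 3 months gives 1, 6 gives 2, 9 gives 3, 12 gives 4. With onset uniform over 24 months and exponential duration, simulation gives k positive records per detected episode; the share of positive records that repeat an episode already counted is 1 − 1/k.

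| Mean duration (months) | k | 1 − 1/k |
|---|---|---|
| 3 | 1.46 | 32% |
| 6 | 2.06 | 51% |
| 9 | 2.49 | 60% |
| 12 | 2.80 | 64% |

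**3. Effect on the conclusion.** One condition of 60, 8 calls, a standard normal predictor, mean episode 6 months, and a log-effect of 0.7 per SD on duration or on onset (exp(0.7) = 2.01). The planned model was a random-intercept logistic model of status at each call. The comparator was a discrete-time first-onset logistic model in which every onset is picked up at the next call. Both used likelihood-ratio tests at two-sided 0.05, with 400 runs per row (396 to 400 usable). Cells show the percentage of runs significant and the median odds ratio.

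| Predictor acts on | Two-year risk | Planned model | First-onset model |
|---|---|---|---|
| neither | 15% | 6.1%, 0.99 | 3.5%, 0.99 |
| neither | 25% | 5.8%, 1.00 | 5.5%, 1.02 |
| duration only | 15% | 12.3%, 1.43 | 3.8%, 1.03 |
| duration only | 25% | 18.8%, 1.57 | 6.2%, 1.00 |
| onset only | 15% | 43.8%, 2.88 | 49.6%, 2.04 |
| onset only | 25% | 61.0%, 2.96 | 72.5%, 2.14 |

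The simulation error on 12% is about √(0.12 × 0.88 / 400) = 1.6 points. At n = 600 (100 runs) the planned model flags a duration-only predictor in 61% and 80% of runs and the first-onset model in 5% and 6%, so the effect is systematic. A repeat at n = 60 gave 12% and 23% against 6% and 10% for duration only, and 40% and 63% against 47% and 69% for onset only. Random-intercept odds ratios are conditional on the person, so their larger size in the onset-only rows is not by itself bias.

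**4. What remains if a first episode is scored only as status at the call.** Longer episodes are more likely to be caught. An exponential episode of mean m, starting uniformly within an interval, is still present at the next call with probability (m/3)(1 − exp(−3/m)).

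- m = 6: 2 × (1 − 0.6065) = 0.787
- m = 6 × 1.65 = 9.9: 3.3 × (1 − 0.7386) = 0.863
- m = 6 / 1.65 = 3.64: 1.212 × (1 − 0.4382) = 0.681

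Per SD, √(0.863 / 0.681) = 1.13. A separate simulation (20% two-year incidence, duration multiplied by 1.65 per SD, no onset effect) gave a first-episode hazard ratio of 1.13, against a call-level odds ratio of 1.43.

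**The case against.** The strongest reply is that the plan has not committed the error. C.2.8 does not say that an episode is scored at every call it spans. A variable for a new episode since the previous call would also be binary and repeated, and a 12-month episode would then score once. That stands: a reader might infer that one long episode is written into the plan as several events, but the documents are silent. Silence still leaves the outcome undefined on either reading.

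A reader might also infer that the model measures persistence and not development. It does not: every positive record needs an onset after entry, and the planned model detected an onset-only predictor in 44% and 61% of runs. Nor do repeat records alone produce false positives; with no effect on either component the rate was about 6%. That one or two chronic participants could dominate the estimate has not been shown.

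Burden over two years is a legitimate exploratory target, and the preliminary result in C.1.2 was of that kind, relating mood to symptoms over 21 months. But the aim says development, so a burden target would need to be stated.

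Finally, nothing in the documents suggests a predictor that acts on duration alone, and most trials of this size would not flag one. That limits the size of the problem but leaves the mismatch between aim and model.

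**Conclusion.** The point holds as a request to define the outcome and match the model to the aim. The scoring of ongoing and recurrent episodes is unspecified. On the natural reading the model mixes onset with duration, and a duration-only predictor is declared significant in roughly 12% to 23% of planned-model runs at 60 per condition, against 4% to 10% with first-onset analysis. First-onset analysis cost no power in the onset-only scenarios tried.

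These figures assume a 15% or 25% two-year onset risk, a mean episode of 6 months and a log-effect of 0.7 per SD. The direction is general; the sizes are not. The aim is exploratory, so no confirmatory conclusion is affected. This is a worthwhile low-cost improvement.

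**What to change.** In C.2.8, for the Exploratory Aim:

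1. Make the lead outcome the first SCID-5-RV-confirmed depressive episode after the experimental session.
2. State in C.2.7 that the SCID-5-RV is scored for any episode since the last call, so that fewer short episodes are missed.
3. Analyse with a discrete-time hazard model (for example complementary log-log) in 3-month intervals. A participant's records end at the first positive call or the last completed call. Keep the separate fits by condition.
4. Keep the mixed-effects repeated-status model as a secondary description of time spent depressed.
5. Count a recurrence only after an intervening negative call.

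**Cost.** Wording, plus a stated look-back for the interview; the calls are unchanged. Information after the first episode leaves the lead analysis. Because the interview is held only when the PHQ-9 is 5 or more, some short episodes that have resolved by the call will still be missed, so the duration effect is reduced and not eliminated.

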Despite the important contribution of inflammation to depression, not all individuals exposed to increased inflammation develop depression.⁵ Less than 30% of patients treated with high doses of IFN- α develop major depressive episodes³; and even when endotoxin is experimentally administered inducing robust systemic inflammation, largely variable increases in depressive symptoms are found.⁴ Indeed, we have shown that depressive responses to endotoxin are far more accentuated in females.¹⁴ In line with our experimental data, the female preponderance in the prevalence of depression is a well-established finding, indicating a higher depression risk in females than males.^{6,7} Moreover, women show higher levels of inflammatory markers,²⁶ and there are well-known sex differences in the prevalence of inflammatory disorders, with females being between 2 and 9 times as likely as males to develop autoimmune disorders.²⁷

However, the female preponderance of depression prevalence decreases in the post-menopausal period,²⁸ and females show a nearly 3-fold decrease in depression incidence from ages 20 to 60. Rates of depression in males, by contrast, remain stable.²⁹ Likewise, levels of systemic inflammation are higher in females than in males, but this sex gap decreases with age.²⁶ Thus, it is unknown whether the vulnerability to inflammation-induced depression evident among younger women remains in later life. If this study shows older females to be more vulnerable to endotoxin-induced depression than older males, the finding will be significant as it would direct prioritization of female older adults for depression prevention. If this study shows no sex differences, the finding will also be significant as it would suggest age-related changes in sex differences and inform future studies on underlying inflammatory and affective mechanisms.

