An institute of medicine (IOM) report in 2001 stated: "Sex matters. Sex, that is, being male or female, is an important basic human variable that should be considered when designing and analyzing studies in all areas and at all levels of biomedical and health-related research The study of sex differences is evolving into a mature science. There is now sufficient knowledge... to allow the generation of hypotheses. The next step is to move from the descriptive to the experimental..."³⁰ *This supplemental study is significant by examining sex differences in inflammation-induced depression leveraging our highly controlled experimental study (R01AG051944, PI [name]), and particularly because, while sex differences in depression and inflammation decrease with aging, it is unknown whether female sex remains a vulnerability factor for inflammation-induced depression in late life. Thus, this application addresses the following strategic goals of the new Trans-NIH Strategic Plan for the Health of Women "Advancing Science for the Health of Women": 1) To advance rigorous research that is relevant to the health of women; 2) To develop methods and leverage data sources to consider sex and gender influences that enhance research for the health of women.*

A.2. Using Age to Interrogate Sex Differences in Vulnerability to Inflammation-Induced Depression

No studies have specifically tested for age differences in vulnerability to inflammation-induced depression. Our prior work has shown that young females (i.e., below the age of 30) are more affectively sensitive to the effects of inflammation than young males, but it is not known if this vulnerability persists into late adulthood. Because late adulthood is characterized by both increased systemic inflammation²⁰ and

decreased depression prevalence,^{16, 17} we hypothesize there may be potential age-related decreases in affective sensitivity to inflammation in older compared to younger females. Notably, major hormonal shifts (e.g., menopause) render older females more biologically similar to older males, which could help explain changes in affective sensitivity to inflammation across the lifespan. If results are consistent with this hypothesis, we will further characterize underlying affective mechanisms by testing sensitivity to both negative and positive affective processes in younger and older women.

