
Finally, we will also evaluate the changes of gene expression in response to endotoxin as a function of sex and age and evaluate *a priori* whether changes in the inflammatory transcriptome are associated with affective response; these analyses will focus upon specialized genomic analyses (T_0 , T_2 , T_4), and utilize methods previously reported by us.^{54,103,104} Quantile-normalized gene expression values will be log2-transformed and subject to GLM analysis to provide maximum likelihood point estimates of differential transcript abundance across group (females vs. males; younger females vs. older females) and condition (endotoxin vs. placebo), which provide maximally replicable inputs into the higher-order set-based bioinformatics analyses. TELiS (Transcription Element Listening System www.telis.ucla.edu) promoter-based bioinformatics analyses will test the hypothesis that PBMC will show alterations by group and condition in global gene expression profiles consistent with increased activity of the proinflammatory transcription factors NF-κB (assessed by

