prevalence of the TRANSFAC V\$NFKAPPAB65_01 nucleotide motif in differentially expressing promoters) and AP-1 (V\$AP1FJ_Q2) in the female groups and the endotoxin condition. We will explore whether female sex, younger age, and endotoxin decrease activity of Type I interferon signaling pathways (V\$ISRE_01, V\$IRF2_01); decrease activity of the anti-inflammatory glucocorticoid receptor (GR) (V\$GR_Q6); and increase activity of CREB transcription factors involved in β -adrenergic signaling by the sympathetic nervous system (V\$CREB_01). Both depression and inflammation are implicated in the regulation of these pathways.^{105,106} Moreover, the human immune system appears to have developed a conserved transcriptional response to adversity (CTRA) that involves up-regulating pro-inflammatory gene expression (e.g., cytokine genes) while conversely down-regulating anti-viral gene expression (e.g., interferon response genes) whenever environmental conditions are experienced as threatening, stressful, or uncertain for an extended period of time.¹⁰⁷ The ratio of response element frequencies in the promoters of up- vs. down-regulated genes are assumed to be a measure of differential activity of transcription control pathways, and (log) ratios will be averaged over 9 different parametric combinations of promoter length (-300, -600, and -1000 to +200 bp upstream of RefSeq-designated transcription start site) and motif detection stringency (TRANSFAC mat_sim values of .80, .90, and .95) to ensure robust results.¹⁰⁸ To identify the primary cellular sources of differentially expressed genes, we will carry out Transcript Origin Analysis.¹⁰⁹ In both TELiS and Transcript Origin Analyses, standard errors will be estimated by 2000 cycles of bootstrap resampling of residual vectors from the linear models used to estimate differential gene expression across groups (sex and age) and condition (controlling for correlated expression across genes).

C.2.9. Justification of Sample Size

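### The genomic analysis asks about response to endotoxin by sex and age, but the contrasts it names are separate group and condition effects, so a resting difference could be read as, or hide, a difference in response

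*Combined protocol and SAP*

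**What the plan says.** The last part of C.2.8 (Statistical Analyses) opens with a response question: "we will also evaluate the changes of gene expression in response to endotoxin as a function of sex and age". It lists samples at T0, T2 and T4. What follows is worded differently:

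- The linear model supplies "point estimates of differential transcript abundance across group (females vs. males; younger females vs. older females) and condition (endotoxin vs. placebo").
- The TELiS hypothesis is that "PBMC will show alterations by group and condition in global gene expression profiles", with NF-κB and AP-1 activity raised "in the female groups and the endotoxin condition".
- The exploratory part will "explore whether female sex, younger age, and endotoxin decrease activity of Type I interferon signaling pathways", listing three effects side by side.
- The bootstrap standard errors for TELiS and Transcript Origin Analysis come from residuals of linear models described only by group and condition.

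No interaction, time term or change from T0 is named anywhere in that paragraph. The preceding paragraph of C.2.8 does name them. For the Aim 1 mixed-model design, carried to Aim 2, it makes the sex-by-condition interaction a key result and crosses it with time for repeated measures. Gene expression is not in the outcome list given there.

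On resting differences, A.1 says that "women show higher levels of inflammatory markers" and A.2 that "late adulthood is characterized by both increased systemic inflammation". A.1 also says that the sex gap in inflammation narrows with age.

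**The concern.** A difference in response to endotoxin is a group-by-condition quantity. Condition is randomised; sex and age are not. A group contrast averaged over the two arms therefore mixes how the groups differ at rest with how they differ in response, and nothing in the contrast separates the two.

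The choice of contrast matters more than usual here. TELiS compares promoters of up-regulated with promoters of down-regulated genes, so the contrast decides which genes enter the analysis at all.

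Two errors are possible. A sex or age difference that is equally present under placebo could be credited to the challenge. In the other direction, the documents place higher resting inflammation in older adults while the study hypothesises greater affective sensitivity in younger women. If transcription follows the same pattern, the two would pull the group term in opposite directions and a real difference in response could disappear. The NF-κB/AP-1 hypothesis also gives no direction for the age contrast, because both of its groups are female.

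**Working it through.** The documents give no power, sample size or alpha for the genomic analysis, so there is no figure to reproduce. The following illustrates the consequence for one normally distributed score.

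**Inputs from the documents.** 20 per cell: C.2.2 gives 40 endotoxin and 40 placebo older adults, stratified by sex (40 of each sex), and 20 and 20 younger women. Samples at T0, T2 and T4 (C.2.6, C.2.8). Two-sided 0.05 is borrowed from C.2.9, where it is stated for Aim 1 depressed mood.

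**Assumptions.** Unit SD; constitutive difference c of 0.25 to 1.0 SD; within-person correlation r of 0.3 to 0.7. The documents give neither c nor r.

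**1. What each term estimates.** Let e be the endotoxin effect in the reference group and d the extra response in the other group. Post-infusion cell means are 0 and e (reference group, placebo and endotoxin) and c and c+e+d (other group).
- Group effect averaged over arms: [c + (c+e+d)]/2 − [0 + e]/2 = c + d/2.
- Group by condition: (c+e+d − c) − (e − 0) = d.

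The interaction removes c at T2 alone. Change from T0 also removes chance imbalance at T0.

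**2. Identical responses (d = 0), T2 only.** SE of the group effect = √(1/40 + 1/40) = 0.224.

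| c (SD) | Group test rejects | Simulated |
|---|---|---|
| 0.25 | 20% | 20–21% |
| 0.5 | 61% | 60–61% |
| 0.8 | 95% | 94–95% |
| 1.0 | 99% | 99–100% |

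In 4,000 simulated trials per setting, group by condition rejected 4.5% to 5.9% of the time, whether at T2 or on T2−T0, for every c and r tried.

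Using more time points with r = 0.5 gives the same picture. Averaging T2 and T4, SE = √(0.75 × 2/40) = 0.194. Adding T0, SE = √(0.667 × 2/40) = 0.183. In 3,000 simulated trials, c = 0.3 gave 33% and 37% rejection, and c = 0.5 gave 73% and 79%. Group by condition on change stayed at 5%.

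**3. Masking (c = −0.3, d = +0.6, r = 0.5).** The post-infusion group effect is −0.3 + 0.6/2 = 0. Over all three times it is −0.3 + (2/3)(0.3) = −0.1. Simulated rejection was 4% and 8%. For group by condition on change (mean of T2 and T4 minus T0), SE = √(0.75 × 4/20) = 0.387 and 0.6/0.387 = 1.55, which is about 34% power (33% simulated).

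**4. Price of the interaction.** At one time point SE = √(4/20) = 0.447, twice 0.224. The difference detectable with 80% power is 2.80 × SE:
- group effect: 2.80 × 0.224 = 0.63 SD;
- group by condition at T2: 2.80 × 0.447 = 1.25 SD;
- group by condition on T2−T0: 2.80 × √[(4/20) × 2(1−r)] = 1.48, 1.25 and 0.97 SD for r = 0.3, 0.5 and 0.7.

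**5. Effect of a baseline covariate.** C.2.8 considers baseline outcome values as covariates when they differ at P<0.15. With T0 always entered (r = 0.5, post-infusion model), false rejection fell from 33% to 15% at c = 0.3 and from 72% to 33% at c = 0.5. That reduces the problem but does not remove it.

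**The case against.** The strongest reply is that the paragraph omits detail rather than specifying a wrong test. It opens with the response question and lists T0. A model across group and condition is compatible with a factorial model that includes the interaction. The same section makes that interaction a key result for the same groups and arms, and the genomic analysis may be meant to inherit it. The paragraph also relies on the team's previously published methods, which may set out the terms. This stands to the extent that a reader might infer that the plan is committed to averaging over placebo and T0, and that constitutive differences would be reported as response differences. The text does not say so; it only leaves that open. Inheritance is not stated either: gene expression is missing from the outcome list, and every operative genomic sentence is worded as parallel effects.

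A reader might also infer that the documents establish a resting difference in expression for both contrasts. They do not. The cited statements concern inflammatory markers or systemic inflammation, not promoter-motif activity in screened healthy volunteers. A.1 says the sex gap narrows with age, and A.2 says menopause makes older women biologically more like older men. The sex contrast is therefore the weaker case and the age contrast the stronger.

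The baseline-covariate rule gives partial protection. However, it is conditional, is worded for females versus males, and leaves residual bias. The rejection rates do not transfer to TELiS, which averages log ratios over nine parameter settings with bootstrap standard errors. Finally, transcriptomics appears in none of the numbered aims nor in the exploratory aim, which limits how much rests on this.

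**Conclusion.** The point holds as a mismatch between the stated question and the stated contrasts. The question is "evaluate the changes of gene expression in response to endotoxin as a function of sex and age"; the contrasts and hypotheses are separate group and condition effects. Followed as written, the group term estimates c + d/2 rather than d. It could therefore present a constitutive difference as a response difference or, most plausibly for age, conceal a real one. That algebra needs no assumption about size. The 20% to 61% rejection at 0.25 to 0.5 SD and the masking example do: they use a single score with assumed effect sizes and correlations, and they show direction and rough scale only. The documents do not support the stronger conclusion that the planned analysis is certain to misattribute resting differences. The correction is worth making because the contrast determines what TELiS analyses and the samples needed are already planned.

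**What to change.** In the genomic paragraph of C.2.8:

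- State that sex and age differences in transcriptional response are tested by group by condition on change from T0 (T2−T0 and T4−T0), or equivalently by group by condition by time, separately for females versus males and for younger versus older females.
- Feed that gene-wise estimate to TELiS and Transcript Origin Analysis, and bootstrap residuals from the same model.
- Reword the NF-κB/AP-1 hypothesis with a direction for each contrast: a larger endotoxin-minus-placebo increase in females than in males, and in younger than in older females.
- Keep the condition main effect as a manipulation check.
- Report T0 group differences separately, labelled as constitutive expression.

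The cost is SAP wording and a changed model contrast; no new samples or arrays are needed. The statistical cost is real. The interaction has about twice the standard error of the group main effect, so fewer group findings should be expected, and the plan should say so.
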